This should be a plain language description. Do not provide scholarly citations. Limit your answer to less than one page, or refer to an attached document with background information that is no more than three pages long.

This is a minimal risk study that involves a clinical trial.

Asthma is most common chronic condition of childhood, affecting over six million US children. Asthma is an incurable, lifelong condition that places children at increased risk for functional impairments, decreased quality of life, school absences, increased healthcare utilization, and irreversible structural airway remodeling. Asthma management involves symptom monitoring and response, trigger avoidance, and timely and appropriate medication use. Unfortunately, fewer than 50% of children with asthma are adherent to asthma management regimens, leading to increased disease morbidity and mortality and potentially irreversible airway damage. Improving pediatric asthma management represents a critical health need.

Children with asthma are missing a voice in their own care. The school-age years (7-11) represent a natural transition in asthma management, as children must assume some responsibility for asthma-related care while they spend increasing time away from parents at school and other extracurricular activities. Developmentally, school-age children are rule-driven, understand right and wrong, and are able to problem solve, which supports their capability to be active participants in their own asthma management. Yet, existing interventions focus on parents alone and use prescriptive approaches, telling the parent what to "do" to the child to manage their asthma. As a result, our current strategies are failing to provide children with asthma and their families the tools they need to manage asthma successfully within the realities of their daily lives. The answer to this problem lies in shared asthma management by the parent-child dyad, with the school-age years (7-11) the ideal developmental period for children to begin sharing responsibility with their parents and establishing lifelong health behaviors.

b. Experience and preliminary work. Briefly describe experience or preliminary work or data (if any) that you, your team, or your collaborators/co-investigators have that supports the feasibility and/or safety of this study.

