2 PARTICIPANTS

2.1 Participants. Describe the general characteristics of the subject populations or groups, including age range, gender, health status, and any other relevant characteristics.

60 children, ages 7-11 years, with persistent asthma and one parent will be recruited for this study. Participants will need to live in King, Pierce, or Snohomish County in Washington State.

Every effort will be made to recruit racial and ethnic minorities; asthma affects all races and ethnicities, with boys and non-Hispanic black children experiencing the highest prevalence. To ensure inclusion of racial and ethnic

minority participants, advertising will particularly target diverse population areas as identified by census tract data.

2.2 Inclusion and exclusion criteria.

a. **Inclusion criteria.** Describe the specific criteria that will be used to decide who will be included in the research from among interested or potential subjects. Define any technical terms in lay language.

Parent/Caregiver Inclusion Criteria

Child's primary caregiver residing with the child (50% or more); ≥ 18 years; speaks and reads English; has a smartphone with data plan; and has a parent-reported asthma responsibility mean score ≤ 2.5 (parent assumes the majority of asthma management responsibility). Participants seeking in person visits must reside within King, Pierce, and Snohomish Counties in Washington State, remote visits will be offered outside of those areas.

Child Inclusion Criteria

1) aged 7-11 years, 2) diagnosis of persistent asthma, defined as a prescription for a daily asthma medication; 3) speak English.

b. **Exclusion criteria.** Describe the specific criteria that will be used to decide who will be excluded from the research from subjects who meet the inclusion criteria listed above. Define any technical terms in lay language.

Parent/Caregiver Exclusion Criteria

None.

Child Exclusion Criteria

Parent report of conditions that impair the child's ability to learn shared-management including: 1) developmental delay (e.g., language < 5 -year level), 2) co-morbid condition (cancer, diabetes, autism); or 3) current asthma exacerbation at the time of recruitment (defined as a prescription for oral corticosteroids) as this is a serious health event and not an opportune time for learning shared management.

2.3 Prisoners.

IRB approval is required in order to include prisoners in research, even when prisoners are not an intended target population.

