expected lung functioning, spirometers use a reference database that requires patient details including age, gender, height, weight. The parent will be instructed to input the study # (instead of name), year of birth (not date) to avoid unnecessary PHI disclosure. The study team will coach the child through spirometry and request that the results be sent to the study team (via email or text). Note, study team will make every effort to perform spirometry outside (weather permitting) and remain socially distanced and advised to wear masks for spirometry, since it is considered an aerosolizing procedure.

Next, individual data collection will commence. Parent participants will be provided an iPad with the electronic instruments preloaded and instructed to complete the instruments to the best of their ability. If questions arise, the study team will answer as needed. The study team will then work 1:1 with the child and assist with instrument completion (reading items, if requested). This technique has been used successfully in [name] other prior dyadic study designs to preclude parental interference in child items. Full instrument descriptions and timepoints are outlined in table below. Estimated time burden: Parent: 50-55 minutes; Child: 40-50 (plus 30-40 if cognitives added).

Assignment

REDCap randomization module will be used to assign dyads to groups using an externally generated block randomization scheme (stratified by sex). After surveys are complete, the study team will assign dyads to intervention or control by selecting “randomize” within REDCap and proceeding with the following, depending on assignment:

Control

Dyads assigned to the usual care control group will be advised of their assignment. An information sheet will be provided that outlines the upcoming data collection sessions (T1 at 8 weeks and T2 and 16 weeks) with compensation amounts. They will be advised to keep the spirometer to use in future visits, and more frequently if they choose. The PI will send the parent an asthma control assessment, based upon spirometry and asthma status questions (C-ACT), with interpretation using the national asthma guideline standards. This report may be shared with the child's health care provider, if desired. Finally, the family will be advised that at the end of the 16 week study period, they will be offered access to the IMPACT system, including the app and wearable device, should they wish to use it.

Intervention

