5.4 Data variables. Describe the specific data that will be obtained (including a description of the most sensitive items). Alternatively, a list of the data variables may be uploaded to **Zipline**.

App usage – login date and duration, management goals selected, anticipated barriers, progress reports, asthma check ins, C-ACT scores, spirometer results, reported medication use.

Document Date & Version

04/29/2021

Version 3.3

Researcher Date & Version

08/16/2021

Version 1.2

APPLICATION IRB Protocol

Page 20 of 56

Instrument details

Construct	Instrument	Time	T0	T1	T2
Demographics					
NINR Demographics	Parent (race, ethnicity, marital status, employment); Child (birthdate, education, race, ethnicity, asthma history) (P)	5	X		
Child Weight, Height	Stadiometer (D) to measure child height (for spirometry), Scale (D) to measure child weight	5	X X	X X	X X
Shared Management					
Asthma Responsibility	Asthma Responsibility Questionnaire (ARQ) (P, C): 10-items, 5-point scale to report asthma management task responsibility, higher scores indicate higher asthma management responsibility for child. Established construct validity; IC reliability $\alpha=.78$ (child), $.84$ (parent).	<5	X	X	X
Asthma Management	Brief Illness Perception Questionnaire (BIPQ) (P,C): 8-item scale to assess beliefs about asthma, with higher scores indicating more burdensome perception.	<5	X	X	X
	Beliefs about Medicines Questionnaire (BMQ) (P,C): 10-item, 5-point scale to assess medication beliefs and concerns, with higher scores indicating higher perceived necessity or concerns.	<5	X	X	X
Self-Efficacy	Asthma Management Self-Efficacy (P, C): 13-items (parent) and 12-items (child), 5-point scale assesses asthma self-efficacy, higher scores indicate higher self-efficacy. Construct validity; IC reliability $\alpha=.87$ (child), $.87$ (parent).	<5	X	X	X
Medication Adherence	Medication Adherence Report Scale for Asthma (MARS-A) (P, C): 10-items, 5-point scale assessing reported asthma controller medication adherence. $M \geq 4.5$ indicates adherence; IC reliability $\alpha=.68$ (child); $.74$ (parent).	<5	X	X	X
Family Functioning	Family Assessment Device (P): 60-item validated instrument using 4-point Likert scale, with higher scores indicating worse levels of family functioning.	10-15	X	X	X
Daytime Function & Health Outcomes					

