Secondary outcome analyses will use mixed model ANCOVAs to assess whether the primary outcome variable means, adjusted for baseline scores, differ between intervention and control groups. We predict a group x time interaction such that shared management and health outcome variables (asthma responsibility score, self-efficacy, medication adherence, control, QOL) will increase to a greater extent in the intervention group. Also pursuant to Aim 2, the dyadic effect of the intervention will be tested with the Actor-Partner Interdependence Model^{103,112} using structural equation modeling with full information maximum likelihood estimation (FIML). First, the pattern of missing data will be tested to determine if it is missing at random. The FIML method is superior to listwise deletion of missing data points in terms of producing less biased estimates. Next, intraclass correlations (ICC) will be examined for parent and child asthma responsibility, self-efficacy, and general health scores. The APIM produces estimates of actor effects (Person A's pretest \rightarrow Person A's posttest) and partner effects (Person A's pretest \rightarrow Person B's posttest). Actor effects are estimated while controlling for partner effects, and vice versa. In these analyses, dyadic interdependence is indicated by statistically significant **partner effects** (e.g., parent pretest \rightarrow child posttest, controlling for child pretest). Intervention condition will be entered into the model as a dummy coded variable. For each measure taken from both parent and child (i.e., self-efficacy, asthma responsibility) two APIMs will be compared; one in which all of the paths from child variables are constrained equal to their respective paths from the parent variables, and one in which all paths are unconstrained and thus free to vary. Comparison of the fit of these two models indicates whether the effects emanating from the parent are significantly different from those emanating from the child. Parent-child dyads in IMPACT are expected to show stronger **partner effects** than those in the comparison group.

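### The between-arm ANCOVA leaves out child age, a plausible predictor collected at T0 but not balanced by the randomisation, so precision may be lost and a chance age gap is only partly corrected

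*SAP*

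**What the plan says.** **Model.** The SAP (Data Analysis, paragraph on secondary outcome analyses) plans mixed model ANCOVAs to test whether outcome means, "adjusted for baseline scores, differ between intervention and control groups". It adds: "We predict a group x time interaction such that shared management and health outcome variables" will improve more under the intervention, and the list includes both primary outcomes. No covariate other than baseline scores is named. Age does not appear in the SAP.

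**Randomisation.** Protocol 5.1 (Assignment) uses an "externally generated block randomization scheme (stratified by sex"). Age is not a stratification factor.

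**Age data.** The instrument table in Protocol 5.4 collects "Child (birthdate, education, race, ethnicity, asthma history") at T0.

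**Rationale.** Protocol 1.8a says: "The school-age years (7-11) represent a natural transition in asthma management, as children must assume some responsibility for asthma-related care" while they spend more time away from their parents. The eligible range in 2.2a is 7 to 11 years.

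**Use of the result.** Protocol 1.5 describes a pilot with 60 dyads. It will report preliminary effect sizes against control for responsibility and self-efficacy (primary) and for adherence, control and quality of life (secondary).

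**The concern.** The Asthma Responsibility Questionnaire scores higher as the child takes on more of the tasks. If children take on tasks as they grow, an older child may have a higher follow-up score than a younger child with the same T0 score. Age would then explain outcome variance that the baseline score does not.

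Two things follow in a trial of this size. The effect size may be less precise than the collected data allow. And if the arms happen to differ in mean age, part of that difference may pass into the estimate. If age is not named in advance, adjusting after an imbalance has been seen becomes a post hoc choice.

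**Working it through.** The documents give no SD, correlation, alpha, power or target effect for these outcomes, so there is no planned figure to reproduce. Everything below uses 60 dyads (Protocol 1.5) and the age range (2.2a), plus stated assumptions: 1:1 allocation, ages uniform from 7 to under 12, and a range of correlations.

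**1. Chance of an age gap**
- SD of age = 5/√12 = 1.443 years.
- SE of the difference in mean age, 30 per arm = 1.443 × √(2/30) = 0.373 years; 95% range ±1.96 × 0.373 = ±0.73 years.
- Chance of a gap of at least 0.5 year = P(|Z| ≥ 0.5/0.373 = 1.34) = 18%.
- At the SAP's 80% retention benchmark (48 dyads, 24 per arm): SE = 0.417, 0.5/0.417 = 1.20, chance 23%.

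**2. Shift from a half-year gap**
- Standardised gap = 0.5/1.443 = 0.346.
- Approximate shift in the baseline-adjusted estimate = rp × 0.346 residual SD, where rp is the partial correlation of age with the follow-up score given baseline. The gap here is the part not already carried by the baseline score.
- rp .2, .3, .4 gives 0.07, 0.10, 0.14 residual SD.
- For scale, the SE of the arm difference is √(2/30) = 0.26 residual SD, so the shift at rp = .3 is about 0.4 SE.

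**3. Net gain from adding age (adjusted difference at one visit)**
- Variance ratio = (1 − rp²) × (n − 4)/(n − 5). The second factor is the price of one degree of freedom: 56/55 = 1.018 at n = 60.

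| rp | Variance ratio, n = 60 | Equivalent dyads (60/ratio) | Variance ratio, n = 48 |
|---|---|---|---|
| 0 | 1.018 | 58.9 | 1.023 |
| .2 | 0.977 | 61.4 | 0.982 |
| .3 | 0.927 | 64.8 | 0.931 |
| .4 | 0.855 | 70.2 | 0.860 |

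- Break-even: 1 − rp² = 55/56, so rp = √(1/56) = .13.
- The gain concerns the adjusted mean difference. A constant age term would not sharpen a purely within-dyad contrast between T1 and T2.

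**4. Plausible size of rp**
- If age correlates equally (rab) with baseline and follow-up, and those two correlate rby, then rp = rab(1 − rby)/√[(1 − rab²)(1 − rby²)].
- Low end, rab = .2, rby = .7: .06/√(.96 × .51) = .09, variance ratio 1.011.
- High end, rab = .5, rby = .5: .25/.75 = .33, variance ratio 0.905.
- In this scenario, then, adding age changes variance by between +1% and −10%. The rp = .4 row lies beyond it.

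**5. Simulation**
- 5,000 trials of 60, rby = .6. Adding age reduced the SE by 0.6-0.7% at rab = .3 and by about 4% at rab = .5.
- Keeping only the lowest 60% of baseline scores, to imitate the responsibility ceiling at entry, made little difference.
- Without age the mean error was at most 0.006 SD, so there was no bias on average.

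**The case against.** The strongest reply is that nothing here is an error. Randomisation makes the estimate unbiased, its standard error already covers chance imbalance, and the baseline score absorbs the part of an age effect that acts through it. No age gradient is documented, and the gain may be nil. All of that stands. It limits the size of the point but does not remove the case for naming a cheap, plausible covariate in advance.

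Several stronger readings are tempting and should be resisted.

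- *The protocol identifies age as what drives responsibility.* It does not. Section 1.8a gives a developmental reason for enrolling the whole 7-11 band and says nothing about a gradient within it. Entry is also limited to dyads where the "parent assumes the majority of asthma management responsibility", which narrows the baseline range.
- *Precision is definitely lost, or an age imbalance is likely.* Neither follows. A gain needs rp above about .13, and 18% for a half-year gap means 82% against it.
- *Each score is adjusted for its own baseline alone, so the other dyad member's T0 score should be added.* The SAP does not define which baseline scores it means, and its Actor-Partner Interdependence Model (APIM) already includes the partner's pretest. For child-reported responsibility, take the stated alphas (.78 child, .84 parent), an assumed stability of .8 and an assumed parent-child true-view correlation of .5. R² then rises only from .389 to .395. That is .006/.611 = 1% of residual variance, or rp about .10, which is below break-even. A saving of about 10% needs true views correlated 1.0.
- *Age should also enter the APIM.* That adds paths to a structural model fitted to about 60 dyads, and nothing in the documents shows a benefit.

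**Conclusion.** The point holds as a modest one. Age is absent from both the between-arm model and the stratification, is collected at T0, and is a plausible predictor on the protocol's own rationale. The omission does not bias the estimate on average. It may cost precision, and it leaves a chance age gap only partly corrected.

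The omission itself is certain. The size of any gain is not: the 18% rests on uniform ages and equal arms, and the shift of 0.07 to 0.14 residual SD and the gain of about 1, 5 or 10 dyads rest on partial correlations for which the documents give no evidence. Under the equal-correlation scenario the result runs from a 1% loss to a 10% gain in variance. A reader might infer that the planned effect sizes are biased or unreliable without age, but the documents do not support that. For a pilot reporting preliminary effect sizes, the value lies in fixing the covariate before the data are seen.

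**What to change.** Add one sentence to the SAP's ANCOVA paragraph: each between-arm model adjusts for the outcome's own T0 score, child age at T0 as a continuous linear term, and sex. Sex belongs there because it is the randomisation stratifier and is also missing from the model. The protocol does not say whose sex; the child's is presumed and should be stated. Naming the outcome's own T0 score also settles which baseline scores are meant.

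Age can be computed from the T0 birthdate, so this needs no new data. It costs one degree of freedom for age (under 2% of variance at n = 60 if age is irrelevant) and one more for sex. The APIM stays as planned, and no partner-baseline term is needed in the ANCOVA.

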1. Determine the feasibility, acceptability and initial efficacy of IMPACT with 60 parent-child dyads in an eight-week pilot randomized controlled trial (RCT).

- a. We will use a priori benchmarks to determine the feasibility of IMPACT based on study eligibility, enrollment, and retention.
- b. Acceptability of IMPACT features and engagement will be determined via exit surveys and semi-structured interviews.
- c. Preliminary effect sizes compared to control will be reported on primary outcomes (asthma responsibility, self-efficacy) and secondary outcomes (medication adherence, asthma control and quality of life).
- d. We will also conduct preliminary testing of dyadic interdependence of asthma responsibility over time.

1.6 Study design. Provide a one-sentence description of the general study design and/or type of methodology.

Your answer will help HSD in assigning applications to reviewers and in managing workload. Examples: a longitudinal observational study; a double-blind, placebo-controlled randomized study; ethnographic interviews; web scraping from a convenience sample of blogs; medical record review; coordinating center for a multi-site study.

This study will use a randomized controlled trial design with two parallel study arms, intervention and control (usual care)

1.7 Intent. Check all the descriptors that apply to your activity. You must place an "X" in at least one box.

This question is essential for ensuring that your application is correctly reviewed. Please read each option carefully.

Descriptor
 1. Class project or other activity whose purpose is to provide an educational experience for the researcher (for example, to learn about the process or methods of doing research).
 2. Part of an institution, organization, or program's own internal operational monitoring.
 3. Improve the quality of service provided by a specific institution, organization, or program.
 4. Designed to expand the knowledge base of a scientific discipline or other scholarly field of study, and produce results that: 
• Are expected to be applicable to a larger population beyond the site of data collection or the specific subjects studied, or• Are intended to be used to develop, test, or support theories, principles, and statements of relationships, or to inform policy beyond the study.

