Dyads assigned to the intervention group will be advised of their assignment. An information sheet will be provided that outlines the intervention tasks (weekly activities) as well as upcoming data collection sessions and compensation amounts. Next, the study team will assist the parent with accessing/downloading the IMPACT app. The family will be encouraged to follow the onboarding screens once downloaded, including pairing the app with the event marker watch (symptom watch) and spirometer device. The symptom watch is a commercially available event marker button that resembles a wristwatch. Children will be taught to press the button when asthma symptoms occur. These events are stored by the watch and synced with the app when connected to the parent phone's Bluetooth.

IMPACT intervention overview:

- Families will be asked to check in on the child's asthma daily (they may use the app to set SMS notifications, if desired) to review symptoms reported by the watch (tracked in the app dashboard).
- They will also be asked to log in weekly to select asthma shared management goals (provided), anticipated barriers, and problem solving. Each subsequent week, dyads will report on their goal progress and select new goals or retain the previous ones.
- To monitor asthma control, families will be prompted to complete the C-ACT (7 item questionnaire) and for the child to complete spirometry. C-ACT and spirometry scores are tracked in the app dashboard (see image)

- The intervention concludes after 8 weeks. The app is configured such that after the 8-week intervention, the goal-setting/monitoring feature is “muted”, but dyads may continue to use the monitoring features (medication use, symptoms, asthma control).

T1 POST-INTERVENTION ASSESSMENT (8 WEEK)

The study team will schedule the T1 data collection session at week 8. The child will be asked to complete spirometry and export results to the study team, as in T0. Dyads will be asked to complete parent and child instruments outlined in the table below, again using the iPads as described above. Families assigned to the intervention will complete short intervention questionnaires and a brief semi-structured interview. Parent: 65-75 minutes; Child: 60-75 (plus 30-40 if cognitives added).

T2 FOLLOW-UP ASSESSMENT (16 WEEKS)

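### The SAP ties the expected benefit to a group x time interaction without listing the time levels; with baseline as the covariate, that term measures persistence after week 8, not benefit

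*SAP*

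**What the plan says.** The SAP's Data Analysis section uses mixed model ANCOVAs "to assess whether the primary outcome variable means, adjusted for baseline scores, differ between intervention and control groups". The next sentence gives the expected result: "We predict a group x time interaction such that shared management and health outcome variables" "will increase to a greater extent in the intervention group". The SAP does not list the levels of time, say whether T0 is a covariate or a response, or name the contrast or visit that carries the treatment effect. Its only other wording on timing, in the Actor-Partner Interdependence Model text, is pretest and posttest.

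Protocol section 5.1 schedules T0 (baseline), T1 (week 8) and T2 (week 16). It also says: "The intervention concludes after 8 weeks". After that the goal-setting feature is muted, while the monitoring features stay open. T1 is labelled the post-intervention visit and T2 the follow-up.

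Aim 1c (protocol section 1.5) promises preliminary effect sizes against control and names no visit. Aim 1 describes an eight-week pilot in 60 dyads.

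**The concern.** An ANCOVA adjusted for baseline normally has the baseline on the right-hand side and only later visits as outcomes. With two later visits, a group x time term asks whether the arm difference changed between week 8 and week 16. That is a question about persistence. A team that checks the stated prediction against that term would find nothing when IMPACT has a lasting benefit, and a term of the wrong sign when the benefit fades after the active phase. It could report the prediction as unmet while the same model shows the benefit.

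At stake is the aim 1c effect size: which coefficient it is, at which visit, and how it is described.

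**Working it through.** **Inputs from the documents.** Three visits (T0, T1, T2), intervention ending at T1, 60 dyads, and a retention benchmark of at least 80%. Neither document gives a power calculation, effect size, SD, correlation or alpha, so there is no figure to reproduce.

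**Assumptions.** 1:1 allocation (30 per arm), SD 1, two-sided 5%, equal correlation r between all visits (0.5, range 0.3-0.7), and an arm difference of 0.5 SD at T1. Call the arm differences at T1 and T2 d1 and d2.

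**Reading A: T0 is the covariate; T1 and T2 are the outcomes.**

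- Group x time = d2 - d1.
- T1 effect = d1.
- T1-T2 average = (d1 + d2)/2.

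If d1 = d2 the interaction is zero, whatever the size of the benefit. If half the effect persists it is 0.25 - 0.50 = -0.25. It is positive only if the benefit grows after week 8.

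Variances per dyad:

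- T1 given T0: 1 - r² = 0.75.
- T1-T2 average given T0: (1 + r)/2 - r² = 0.50.
- T2 minus T1: 2(1 - r) = 1.00.

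Multiplying by 2/30 and taking the square root gives standard errors of 0.224, 0.183 and 0.258. Results for a sustained 0.5 SD benefit:

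| Quantity | Estimate ± 95% half-width | Rejection rate, r = 0.5 (r = 0.3 to 0.7) |
|---|---|---|
| T1 difference | 0.50 ± 0.45 | 59% (51-76%) |
| T1-T2 average | 0.50 ± 0.37 | 76% (72-89%) |
| Group x time | 0.00 ± 0.52 | 5% (5-5%) |

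Simulation agrees: 58-59%, 76% and about 5%. At 0.8 SD sustained, T1 rejects 94% of the time and the interaction still 5%. If half the effect persists, the interaction rejects 16% of the time (13-24%), and in the predicted direction 0.3% or less. At 24 per arm (80% of 30) with a sustained 0.5 SD, the rates are 49% for T1, 66% for the average and 5% for the interaction.

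**Reading B: T0 is a level of time.** The interaction now reflects benefit.

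- *Levels T0 and T1.* The interaction is the arm difference in change. Its variance is 2(1 - r) = 1.00, against 0.75 for the baseline-adjusted T1 difference. Power is about 48%, against about 59% for the adjusted difference.
- *Levels T0, T1 and T2.* The 2-df interaction rejects about 49% of the time (37-73%) under a sustained benefit if the model has no baseline-by-time term, and 66% (60-81%) if it has one.

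In both cases the SAP's baseline adjustment makes T0 a covariate as well as an outcome.

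**T1 or the average as headline.** If a fraction p of the T1 effect remains at T2, the two have equal power when (1 + p)/2 = √(0.50/0.75) = 0.816, so p = 0.63 (0.57-0.68 over the range of r). Below that, T1 has more power; above it, the average does.

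**The case against.** The best defence is the SAP's own wording. An increase has to be measured from somewhere, and baseline is the obvious origin. The SAP also expects responsibility scores to rise over time in the intervention arm, and its dyadic model speaks of pretest and posttest. On that meaning T0 is a time level and a lasting benefit produces the predicted interaction. This stands as a possible reading, so the zero result is conditional. The text does not settle the matter, because it also calls the means baseline-adjusted.

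Second, the sentence before the prediction plans a comparison of adjusted means between arms, which would show the benefit on reading A. That also stands. A reader might infer that the planned model cannot detect a lasting benefit; the documents do not support that.

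Third, a reader might infer that with T0 as a level the adjusted-mean comparison understates a lasting effect by a third, since averaging 0, d and d gives 2d/3. The SAP nowhere says the means are averaged over visits, still less over the pre-treatment visit, and a mixed model gives adjusted means by visit. Nor is the adjusted T0 difference zero by construction: with a common baseline slope it is zero only in expectation, and exactly zero only with a baseline-by-time term.

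Finally, this is a pilot. Its benchmarks concern feasibility and acceptability, its effect sizes are called preliminary, and the 5% rate only restates that a null contrast rejects at alpha. This limits the harm but leaves the ambiguity in a stated deliverable.

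**Conclusion.** The point holds in a limited form. The SAP leaves the time levels open and attaches its prediction to a term that, on the ordinary ANCOVA reading, equals d2 - d1. That result is algebra and depends on no assumed value. Under a sustained benefit of any size the prediction fails; under a fading one the sign is reversed. If T0 is a time level the term is a legitimate test of benefit, but the specification is internally awkward, and at T1 it is less precise than the baseline-adjusted difference (about 48% against 59% power).

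The rejection rates rest on an assumed 0.5 SD, equal correlations of 0.3-0.7 and 30 per arm. They illustrate the point and do not forecast this trial. The consequence is confined to how the aim 1c effect size is estimated and described; no decision rule depends on either test.

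**What to change.** Amend the SAP's mixed-model paragraph:

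1. State that T0 is the covariate and that T1 and T2 are the repeated outcomes.
2. Replace the group x time prediction with baseline-adjusted arm differences and 95% CIs at T1 and at T2, from the same model.
3. Read T2 minus T1 only as persistence after week 8.
4. Name in advance which quantity heads the aim 1c report. This is the sponsor's estimand choice. T1 fits the eight-week and post-intervention labels; the T1-T2 average is the alternative, and whichever is not chosen can be shown as supportive.

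The cost is wording only: no new data, visits or models. The one trade-off lies in item 4. If the benefit fully persists, T1 gives a wider interval than the average (±0.45 against ±0.37 SD) and less power (59% against 76%). It has more power only if less than about 63% of the week-8 effect remains at week 16.
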